14.2.2. Reporting Procedures for Adverse Events

AEs occurring to a participant will be recorded in the main research file (REDCap) and the participant's clinical records, if appropriate. Reports of AE should be submitted as soon as possible to the local PI and CIs after being identified by a researcher and within the next seven working days.

Based on previous safety reports and research experience with DD+, a low likelihood of a 'related' event is expected. Due to the nature of the intervention and the low risk of AE, causality assessment will be jointly conducted by the local PI and CI within the next 30 working days after the report.

14.3. Urgent Safety Measures

In the case of urgent safety measures being required, the local PI will inform the CIs and the REC/IRB of the event as per REC/IRB and other relevant requirements and guidelines.

14.4. Annual Safety Reporting

The local PI will send over annual reports as required by the REC/IRB using their existing templates and guidelines.

14.5. Overview of the Safety Reporting Responsibilities

The PI ([name]) will ensure that safety monitoring and reporting are conducted in accordance with the requirements of the REC and any other relevant organisations/institutions that are involved in overseeing and monitoring research activities.

15. STATISTICS AND ANALYSIS

An independent statistician, blinded to participant allocation status, will conduct all analyses. Blinding will be maintained throughout data cleaning and statistical procedures to minimise bias.

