10. STUDY DESIGN

10.1. General Design

To assess the effectiveness and implementation context of DD+, we will conduct a Hybrid I Randomised Controlled Trial (RCT) using a mixed-methods approach (11,12,40). A health economic analysis will also be included to evaluate the cost of delivering the intervention in the local setting. Effectiveness will be assessed through an RCT, implementation will be evaluated through a descriptive mixed-methods implementation study, and cost-effectiveness will be assessed through an embedded health economic analysis.

Patients in selected HC (Health Centres) will be pre-screened for chronic physical and mental health conditions. Those who meet the initial criteria will be recruited. After accepting to participate and signing informed consent, they will undergo full screening for physical and mental health conditions and QoL. Patients with co-existing physical and mental NCD will be randomised to the active intervention or the control group. Healthcare practitioners (contracted research study professional/staff) trained in DD+ will deliver the assigned intervention to each active intervention participant once per month for six months. Participants allocated to the control group will continue their usual or routine care as established by the HC professionals and procedures. Participants in the control group will be contacted periodically by phone (**Figure 1**).

[figure not shown]
Participants in both study arms will be assessed for outcome measures at baseline, 6, and 12 months. **Table 2** displays the timing and content of study procedures, including interventions, assessments, and interviews across all study visits.

To assess the **implementation context**, a mixed-methods approach will be used, with the following steps:

- a) At the 6-month assessment, all patients in the intervention arm will complete the AIM and IAM scales.
- b) At the 6-month assessment, a subsample of the intervention group participants will be invited to individual interviews to enhance explanatory power and to assess additional implementation criteria, including fidelity, adoption, and feasibility.

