12.8. Blinding and code-breaking

Due to the nature of the DD+ intervention and the usual care control group, patients cannot be blinded to the intervention. Researchers responsible for recruitment, screening, baseline assessment, and scheduling intervention appointments will be unblinded. Researchers conducting outcome evaluations will be blinded to participant allocation, and participants will be instructed not to disclose details of their allocation to the research team at any time during the study.

Blinded statisticians will perform statistical analysis. Qualitative interviews and analysis will be conducted by unblinded researchers.

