15.8. Secondary Objective (Feasibility)

For the participants, the AIM and IAM will be administered at 6 months. Descriptive statistics will be presented for each instrument means and standard deviations (SD) will be reported for approximately symmetric distributions, and medians and interquartile ranges (IQR) for skewed distributions. No formal statistical hypothesis testing is planned.

For healthcare practitioners and leaders, the AIM, IAM, and FIM will be administered at baseline and at 6 months. Each measure will be summarised using means and SD when the distribution is approximately symmetric; otherwise, medians and IQR will be reported. Change scores between the baseline and 6-month assessments will be calculated and reported descriptively.

Feasibility of Intervention Completion will be calculated as the number of participants who agreed to participate, provided informed consent, were allocated to the active treatment, and completed the intervention as planned, divided by the total number of participants who provided informed consent.

No formal statistical hypothesis testing will be conducted.

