15.9. Secondary Objective (Effectiveness)

Mixed-effects models will be used to evaluate the effect of the intervention on the secondary outcomes (see **Table 1**) at 6- and 12-month follow-up assessments. Analyses will be conducted under the intention-to-treat principle. Each model will include fixed effects for treatment group (intervention vs control), time, the baseline score of the corresponding outcome, and other relevant baseline covariates. A random effect for clinical professional group (cluster) will be included to account for intragroup correlation. The models will report adjusted mean differences between groups, with corresponding 95% confidence intervals (CIs) and p-values.

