15.11.7. Analysis of cost-effectiveness

We will compute the ICER as the additional cost per additional QALY gained ($\Delta C/\Delta E$). Interpretation will use Colombia-relevant willingness-to-pay (WTP) benchmarks. Specifically, we will present cost-effectiveness acceptability curves (CEACs) across a WTP range and highlight the empirically estimated Colombia threshold of about US\$5,181 per QALY (\approx COP 17 million in 2019 prices) from Espinosa et al. (55) (IETS) updated to the study price year (2025) using DANE CPI. DIALOG+ will be described as cost-effective when the ICER lies below a WTP value deemed acceptable in Colombia, and we will report the probability of cost-effectiveness at the updated reference threshold and other policy-relevant WTP points.

Differences between trial arms in costs and outcomes will be estimated on an intention-to-treat basis, initially unadjusted and subsequently adjusted for pre-specified baseline covariates. If participant characteristics differ systematically between arms, adjusted models will include age, sex, NCD condition group (hypertension/obesity/T2DM), mental health condition group (anxiety, depression or alcohol misuse), baseline utility (EQ-5D-5L), baseline MANSA and WHOQOL-BREF, baseline total cost, and site (fixed effects).

Incremental costs will be estimated using mixed-effects generalized linear models appropriate for skewed data (primary: Gamma family with log link, or log-normal), including by random effect in the model for healthcare practitioners who delivered DIALOG+ considering clusters. Incremental cost-effectiveness will be estimated with linear mixed models including the same covariates.

Based on the results for quality of life, blood pressure control, glycated hemoglobin, and within-trial cost-effectiveness, we plan to conduct a modeled cost-effectiveness extension study over a 5-year time horizon from the healthcare perspective. In addition, a budget impact analysis with the same horizon will be carried out to support acceptability among decision-makers in the country.

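### The protocol claims that all statistical analyses stay blinded to allocation, but the feasibility analyses in 15.8 reveal the arm and would unblind the analyst before the 12-month effectiveness analysis

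*Protocol*

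**What the plan says.** Protocol Section 15 opens with two unqualified statements: "An independent statistician, blinded to participant allocation status, will conduct all analyses", and "Blinding will be maintained throughout data cleaning and statistical procedures to minimise bias". Section 12.8 says the same in the plural ("Blinded statisticians will perform statistical analysis") and makes one exception: "Qualitative interviews and analysis will be conducted by unblinded researchers". No point is given at which analyst blinding ends.

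The quantitative analyses under the same Section 15 include:

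- **Patient AIM and IAM.** Section 10.1 has it that at 6 months "all patients in the intervention arm will complete the AIM and IAM scales". Sections 13.3.1 and 13.4 also restrict these scales to the intervention arm among patients. Section 15.8 summarises them.
- **Completion proportion.** The numerator in 15.8 counts consenting participants who "were allocated to the active treatment, and completed the intervention as planned".
- **Cost model.** Section 15.11.7 includes a "random effect in the model for healthcare practitioners who delivered DIALOG"+.

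Section 16 acknowledges that patients know their allocation and that this may inflate the reported quality-of-life effect. It offers the blinding of outcome assessors and statisticians as the counterweight.

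**The concern.** A statistician told to stay blinded through cleaning and analysis is also given, on the protocol's wording, data that only one arm can produce. If those data reach the person who runs the effectiveness models, the blinding is nominal.

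This matters for three reasons. The primary outcome is self-rated by unblinded patients, so the remaining safeguards carry weight. The protocol also leaves some modelling choices open: the secondary models adjust for the baseline score "and other relevant baseline covariates", the imputation model in 15.4 may add measures judged relevant to the objective, and Section 16 speaks of adjusting the primary and secondary analyses for covariates that it does not list. Finally, an unqualified claim of blinded analysis is likely to be carried into the trial report, where it would not be accurate.

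**Working it through.** No figure is in dispute, so the check is mainly a comparison of sections. Arithmetic is needed only to show how far one unmasked field reaches.

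**1. Scope of the claim.** Section 15 covers every analysis and every stage from cleaning onward. Section 12.8 removes only qualitative work. Sections 15.8 and 15.11 are quantitative and sit under the heading of Section 15, so both fall inside the claim.

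**2. Which analyses need the arm.**

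| Analysis | Section | Why it reveals the arm |
|---|---|---|
| Patient AIM/IAM at 6 months | 10.1, 13.3.1, 13.4, 15.8 | Values exist for DD+ patients only |
| Completion proportion | 15.8 | Numerator is defined by allocation to DD+ |
| Cost model | 15.11.7 | Cluster term is the practitioner who delivered the intervention; Section 16 has a trial clinician deliver it to the active group, while controls receive phone calls |

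The first two are enough. Table 2 does not mark its AIM and IAM rows as intervention-only, but the text of the three sections cited is explicit.

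**3. How far one record reaches.** The protocol's sample size is 90 per group before attrition. With 20% attrition, 90 / 0.8 = 112.5, rounded up to 113 per group, and 2 × 113 = 226, as stated. Assume that the 20% attrition applies equally to both arms at 6 months:

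- DD+ patients with AIM/IAM data: 113 × 0.8 = 90.4, about 90. These are identified directly.
- Controls with AIM/IAM data: 0.
- Participants without 6-month data: 113 − 90 = 23 per arm, 46 in total. AIM/IAM say nothing about these directly.

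Every effectiveness model (15.7, 15.9) and the imputation model (15.4) needs a treatment variable. If it is masked as A or B, a single AIM/IAM record shows which letter is DD+. That decodes all 226 participants, including the 46. The attrition assumption affects only the direct count, since one record suffices.

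**4. Timing.** Patient AIM/IAM are collected at the same 6-month visit as the primary MANSA. Section 15.5 has data processed and analysed after the 6-month follow-up and again after the 12-month follow-up. The sequence is then:

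1. 6-month MANSA analysis: can be done blinded if the DD+-only fields are held back.
2. 6-month feasibility analysis (15.8): reveals the arm codes.
3. 12-month cleaning and the 12-month models of 15.9: done by an analyst who already knows the arms.

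Step 3 contradicts Section 15 even if step 1 is handled perfectly. No section assigns step 2 to someone else or delays it.

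**The case against.** The strongest reply is that this is one over-broad sentence. Masked codes, withheld fields and the moment of unblinding usually belong in a statistical analysis plan or data management plan, and that plan is not at hand. This is right about the mechanics. It does not rescue the statement, because the protocol asserts blinding for every analysis, and no staging plan can make that true of 15.8.

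A reader might also infer more than the documents support:

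- **That no analysis can be blinded.** Not so. The 6-month MANSA analysis can be run and locked on masked codes before the DD+-only fields are opened.
- **That the clinician term unmasks the primary model.** Table 7 lists Clinician ID at baseline as well as at follow-up, with no arm restriction, and 15.4 counts clinician among the baseline covariates. It may be the usual-care clinician. Only 15.11.7 names the deliverer, so Clinician ID is supporting evidence at most.
- **That DD+ cost forms or session records must reach the statistician.** Table 7 has the research team calculate the DD+ costs, and it lists no per-session attendance field. The completion numerator could be supplied as a count.
- **That a single person handles everything.** Section 12.8 speaks of several statisticians. They are all described as blinded, so the plural does not resolve the conflict.
- **That blinding is declared to protect covariate choice.** The protocol says only that it is meant to minimise bias and, in Section 16, overestimation. For the primary outcome, 15.7 specifies treatment, baseline MANSA and a clinician random effect; only its lay summary refers to further covariates. The open list is in 15.9.

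These limits narrow the point. They leave the conflict between Sections 12.8 and 15 on one side and 15.8 on the other, and the consequence for the 12-month analysis.

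**Conclusion.** The point holds in limited form. The claim that all statistical analyses are blinded from cleaning onward is incompatible with 15.8 and with the deliverer term in 15.11.7. If 15.8 is run in the 6-month round by those who also analyse the 12-month data, the arm of all 226 participants is known to them before the 12-month data are cleaned.

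This rests on two assumptions: the arm variable is held in coded form alongside the AIM/IAM data, and 15.8 follows the schedule of 15.5. Nothing in the protocol says otherwise on either count.

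The effect is on the credibility of a stated bias control. No bias is quantified, and the sample size, the estimator and the error rate do not change. The correction is worth making before the 6-month data are opened, because it is cheap then and cannot be made afterwards.

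**What to change.** 1. In Sections 12.8, 15 and 16, limit the blinding claim to the effectiveness analyses in 15.7 and 15.9.
2. Fix the covariate list, the imputation model and the code for both the 6-month and the 12-month models on masked arm codes. Do this before AIM/IAM, completion data or any identifier of the DD+ deliverer is released to the analyst.
3. Describe 15.8 and the DD+-specific parts of 15.11 as unblinded.
4. For the 12-month analysis, choose one of two routes: hold the 15.8 patient data from the effectiveness statistician until the 12-month dataset is cleaned and locked, or have existing unblinded research staff produce those summaries, which are purely descriptive. If neither is done, do not claim blinding for 12-month cleaning.
5. State what Clinician ID in Table 7 refers to. If it is the DD+ deliverer, treat it as one of the withheld fields.

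The detailed release steps can sit in the statistical analysis plan. The cost is a few sentences of protocol text, a staged data release and a narrower blinding claim. Patients, sample size and outcomes are unaffected.

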15.1. Study Variables

Table 7 presents the study variables, their measurement scales, operationalisation, and the time points at which each variable will be collected.

Table 7. Study Variables

| Variable | Measurement Scale | Operationalisation | Follow-up |
|----------------------------|------------------------------|--|-------------------------------|
| Date of assessment | Date | Date on which the assessment is conducted, recorded in the format DD/MM/YYYY | Baseline, 6 months, 12 months |
| Health centre ID | Nominal | Unique three-digit code identifying the health centre | Baseline, 6 months, 12 months |
| Participant ID | Nominal | Unique three-digit code assigned to the participant | Baseline, 6 months, 12 months |
| Interviewer ID | Nominal | Unique three-digit code assigned to the interviewer | Baseline, 6 months, 12 months |
| Clinician ID | Nominal | Unique three-digit code assigned to the clinician | Baseline, 6 months, 12 months |
| Date of birth | Date | DD/MM/YYYY | Baseline |
| Sex | Nominal | 1. Male 2. Female 3. Prefer not to say | Baseline |
| Spanish literacy | Ordinal | 1. Can read and write 2. Can read but not write 3. Cannot read or write | Baseline |
| Marital status | Nominal | 1. Single 2. Cohabiting 3. Divorced or separated 4. Married 5. Widowed | Baseline |
| Place of residence | Nominal | 1. Hamlet/Rural district (corregimiento) 2. Rural village (Vereda) 3. Municipal centre (Cabecera municipal) 4. Indigenous reserve (Resguardo indígena) 5. Other (specify) | Baseline |
| Ethnic Self-Identification | Nominal | 1. Indigenous (Indígena) 2. Black, Afro-Colombian, Raizal or Palenquero (Población Negra, Afrocolombiana, Raizal y Palenquera) 3. Gitano (Gitano(a) o Rrom) 4. No ethnic group (Ningún grupo étnico) | Baseline |
| Indigenous group | Text | If the participant identifies as Indigenous, they must provide the name and a description of the Indigenous group or community to which they belong (open-ended response) | Baseline |
| Social status or situation | Nominal (multiple selection) | 1. Farmer 2. Victim of armed conflict 3. Displaced due to violence 4. Community leader 5. None 6. Other (specify) | Baseline |
| Household composition | Nominal (multiple selection) | 1. Lives alone 2. Parents 3. Children 4. Other relatives 5. Friends 6. Partner 7. Others (specify) | Baseline |
| Current health conditions | Nominal (multiple selection) | 1. None 2. Diabetes 3. Obesity or overweight 4. Hypertension 5. Dyslipidaemia 6. Asthma 7. COPD 8. Tuberculosis 9. Hepatitis 10. Cancer 11. Poor dental health 12. Alcohol consumption 13. Anxiety 14. Depression 15. Bipolar disorder 16. Other (specify) | Baseline |
| Health insurance scheme | Nominal | 1. Uninsured 2. Subsidised scheme 3. Contributory scheme 4. Special scheme 5. Complementary plan or private insurance 6. Don't know | Baseline |
| Education degree | Ordinal | 1. No formal education 2. Incomplete primary 3. Complete primary 4. Incomplete secondary 5. Complete secondary 6. Technical or vocational qualification 7. University degree 8. Other (specify) | Baseline |

| | | | |
|---|-------------|--|-------------------------------|
| Main occupation | Nominal | 1. Employed 2. Studying 3. Housework 4. None 5. Other (specify) | Baseline |
| Type of work | Nominal | 1. Full-time 2. Part-time 3. Unpaid work (domestic, caregiving, volunteer) 4. Not applicable | Baseline |
| HbA1c (Glycated hemoglobin) | Ratio | Blood test measuring % of glycated hemoglobin | Baseline, 6 months, 12 months |
| Systolic Blood Pressure (SBP) | Ratio | Measured in mmHg | Baseline, 6 months, 12 months |
| Diastolic Blood Pressure (DBP) | Ratio | Measured in mmHg | Baseline, 6 months, 12 months |
| Blood Pressure Control | Dichotomous | Achieving <130/80 mmHg | Baseline, 6 months, 12 months |
| Height | Ratio | Measured in meters or centimeters | Baseline, 6 months, 12 months |
| Weight | Ratio | Measured in kilograms | Baseline, 6 months, 12 months |
| BMI | Ratio | Calculated as weight (kg) / height ² (m ²) | Baseline, 6 months, 12 months |
| Waist Circumference | Ratio | Measured in centimeters (cm) | Baseline, 6 months, 12 months |
| AUDIT-C (Alcohol Use Disorders Identification Test) Score | Interval | A brief 3-item screening tool assessing alcohol use: drinking frequency, typical quantity, and frequency of heavy drinking (six or more drinks per occasion). Each item is scored 0–4; scores are summed to give a total of 0–12. Higher scores indicate greater alcohol consumption and increased risk of alcohol-related problems | Baseline, 6 months, 12 months |
| Manchester Short Assessment of Quality of Life (MANSA) | Interval | Measure of subjective quality of life across multiple life domains. It comprises 16 items, including 12 subjective ratings of satisfaction across core life domains, each scored on a 7-point Likert scale (1 = extremely negative, 7 = extremely positive), and four objective yes/no items on social contact, victimisation, and legal issues. The overall score is the mean of the 12 satisfaction ratings, with higher values indicating better perceived quality of life. | Baseline, 6 months, 12 months |
| Objective Social Outcomes Index (SIX) | Ordinal | The index covers four domains: employment (0–2), accommodation (0–2), living arrangements (0–1), and friendship/social contact (0–1). The total score is obtained by summing the domain scores, yielding a range from 0 to 6, with higher values indicating better objective social outcomes. | Baseline, 6 months, 12 months |
| Patient Health Questionnaire-8 (PHQ-8) | Interval | An 8-item validated self-report screening measure of depressive symptoms over the past two weeks. Each item is scored on a 4-point scale (0 = not at all, 3 = nearly every day), resulting in a total score ranging from 0 to 24, with higher values indicating greater depressive symptom severity. | Baseline, 6 months, 12 months |
| Generalised Anxiety Disorder-7 (GAD-7) | Interval | A 7-item validated self-report screening measure of anxiety symptoms over the past two weeks. Each item is scored on a 4-point scale (0 = not at all, 3 = nearly every day), resulting in a total score ranging from 0 to 21, with higher values indicating greater anxiety symptom severity. | Baseline, 6 months, 12 months |
| WHOQOL-BREF | Interval | 26-item validated tool assessing quality of life across four domains (Physical health, Psychological health, Social relationships, Environment) and two overall items on general QoL and health satisfaction. Each item scored on a 5-point Likert scale (1 = very poor/very dissatisfied, 5 = very good/very satisfied); domain scores | Baseline, 6 months, 12 months |

| | | | |
|--|----------|---|---|
| | | are calculated according to WHO guidelines and transformed to a 0–100 scale, with higher scores indicating better quality of life. | |
| Acceptability of Intervention Measure (AIM) - Score | Interval | Comprises 4 items assessing the acceptability of an intervention: approval, appeal, liking, and welcoming of the intervention. Each item is rated on a 5-point Likert scale: 1 (Completely disagree) to 5 (Completely agree). Total score is calculated by averaging the item scores. | Baseline, 6 months |
| Intervention Appropriateness Measure (IAM) - Score | Interval | Comprises 4 items assessing the perceived appropriateness of the intervention: whether it seems fitting, suitable, applicable, and a good match. Rated on a 5-point Likert scale: 1 (Completely disagree) to 5 (Completely agree). Total score is calculated by averaging item scores. | Baseline, 6 months |
| Feasibility of Intervention Measure (FIM) - Score | Interval | Comprises 4 items assessing the feasibility of the intervention: whether it seems implementable, possible, doable, and easy to use. Items are rated on a 5-point Likert scale: 1 (Completely disagree) to 5 (Completely agree). Scores are averaged across items to obtain a total score. | Baseline, 6 months |
| Feasibility of Intervention Completion | Ratio | Feasibility was measured as the proportion of participants who agreed to participate, provided informed consent, were allocated to the active treatment, and completed the intervention as planned, relative to all those who initially agreed to participate and consented. | 6 months |
| Death status | Nominal | Has the individual passed away by the end of the follow-up period? (Yes/No). This is essential for determining the QALY value, as it implies a quality-of-life value of 0 for that individual. | 12 months |
| Costs of health service use, medication and productivity lost. Out-of-pocket expenses. | Ratio | In the CSRI instrument, we collect participants' use of inpatient hospital service, use of health care services, current medication, family support, out-of-pocket expenses and employment. | Baseline, 6 months, 12 months |
| Costs of DIALOG+, and costs of supervision and training to health professional | Ratio | The Health Economics Inventory forms | Training phase, implementation and monthly in the intervention arm. The research team will calculate costs. |

